#### **3.3.2 Treatment assignment**

- 8-16 weeks after completion of curative intent therapy for locally advanced squamous cell carcinoma of the head and neck patients will be randomized to receive everolimus 10 mg or placebo
- Treatment assignment will be double-blinded. Unblinding will occur at the conclusion of the study (approximately 2 years after completion of accrual) or if required for patient safety
- Expected treatment duration is 1 year from day 1 of everolimus or placebo administration
- Randomization will be stratified for disease stage and type of local therapy (IVa surgical vs. IVa non-surgical vs. IVb) as well as treating institution.
- A secure online registration interface has been developed to register patients, and is integrated with the randomization component, as well as data collection and storage system. This type of an interface has been used successfully in other Head and Neck cancer clinical trials at the University of Chicago (e.g. DeCIDE).

- Stratified randomization sequences will be generated using the method of permuted blocks. At the time of patient registration an electronic notification will be sent to the study pharmacist. To randomize this patient, the pharmacist will login into the registration system, which will provide the randomized treatment assignment. Only the pharmacist will have access to the treatment assignment to maintain the blinding.

### 3.3.3 Concomitant therapy

Patients will be instructed not to take any additional medications (including over-the-counter products) during the course of the study without prior consultation with the investigator. At each visit, the investigator will ask the patient about any new medications he/she is or has taken after the start of the study drug.

All Concomitant medications/Significant non-drug therapies taken  $\leq$  30 days prior to start and after start of study drug, including physical therapy and blood transfusions, should be recorded.

The following restrictions apply during the entire duration of the study:

- No other investigational therapy should be given to patients.
- No anticancer agents other than the study medication should be given to patients. If such agents are required for a patient then the patient must first be withdrawn from the study.
- Oral contraceptives in preclinical and clinical data have shown everolimus to have CYP3A4 inhibitory activity rather than induction activity, induction of metabolism of contraceptive hormones by everolimus is unlikely. Consequently, administration of everolimus should not reduce the efficacy of oral contraceptives.
- Growth factors (e.g. G-CSF, GM-CSF, erythropoietin, platelets growth factors etc.) are not to be administered prophylactically but may be prescribed by the investigator for rescue from severe hematologic events, if this is thought to be appropriate.
- Concurrent administration of Everolimus and strong CYP3A4 inhibitors (such as ketoconazole, itraconazole, ritonavir) and inducers (such as rifampin, rifabutin) should be avoided. Provided there is no alternative treatment available, patients should be closely monitored for potential toxicities.
- Concurrent administration of Everolimus and moderate CYP3A4 inhibitors (such as erythromycin, fluconazole, calcium channel blockers, benzodiazepines) and moderate CYP3A4 inducers (e.g. carbamazepine, phenobarbital, phenytoin) should also be avoided if possible, or used subject to caution (e.g. increased frequency of safety monitoring, temporary interruption of Everolimus).
- Competitive inhibition could occur when Everolimus is combined with drugs which are also CYP3A4 substrates. Therefore caution should be exercised in such cases.
- Co-administration with substrates, inducers, or inhibitors of P-glycoprotein should be avoided, if possible, or used subject to caution (e.g. increased frequency of safety monitoring, temporary interruption of Everolimus).
- Grapefruit and grapefruit juice affect cytochrome P450 and P-glycoprotein activity and should therefore be avoided.

- In addition, patients should avoid Seville oranges and star fruit, as well as the juice of these fruits, which are potent CYP3A4-inhibitors.
- No chronic treatment with systemic steroids or another immunosuppressive agent. Topical or inhaled corticosteroids are allowed.
- Everolimus may affect the response to vaccinations making the response to the vaccination less effective. Live vaccines should be avoided while a patient is treated with Everolimus.

### **Inhibitors of CYP3A4 and/or PgP**

Co-administration with strong inhibitors of CYP3A4 (e.g., ketoconazole, itraconazole, ritonavir) or P-glycoprotein (PgP) should be avoided.

Co-administration with moderate CYP3A4 inhibitors (e.g., erythromycin, fluconazole) or PgP inhibitors should be used with caution. If patient requires co-administration of moderate CYP3A4 inhibitors or PgP inhibitors, reduce the dose of everolimus to half the currently used dose. Additional dose reductions to every other day may be required to manage toxicities. If the inhibitor is discontinued the everolimus dose should be returned to the dose used prior to initiation of the moderate CYP3A4/PgP inhibitor.

Seville orange, star fruit, grapefruit and their juices affect P450 and PgP activity. Concomitant use should be avoided.

### **Inducers of CYP3A4 and/or PgP**

Avoid the use of strong CYP3A4 inducers. If patient requires co-administration of strong CYP3A4 inducers (i.e., phenytoin, carbamazepine, rifampin, rifabutin, phenobarbital, St. John's wort), an increase in the dose of everolimus up to twice the currently used daily dose should be considered, using 2.5mg - 5mg increments. Enzyme induction usually occurs within 7-10 days, therefore everolimus dose should be increased by one increment 7 days after the start of the inducer therapy. If no safety concerns are seen within the next 7 days, the dose can be increased again one additional increment up to a maximum of twice the daily dose used prior to initiation of the strong CYP3A4 inducer.

This dose adjustment of everolimus is intended to achieve similar AUC to the range observed without inducers. However, there are no clinical data with this dose adjustment in patients receiving strong CYP3A4 inducers. If the strong inducer is discontinued the everolimus dose should be returned to the dose used prior to initiation of the strong CYP3A4/PgP inducer.

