### **3.3 Treatments**

#### **3.3.1 Everolimus Administration**

The study drug Everolimus or placebo will be self-administered (by the patients themselves). The investigator will instruct the patient to take the study drug exactly as specified in the protocol. Everolimus /placebo will be administered orally as once daily dose of 10 mg (two 5 mg tablets) continuously from study day 1 until progression of disease, unacceptable toxicity, or 1 year from start of therapy. Patients will be instructed to take Everolimus /placebo in the morning, at the same time each day. Everolimus /placebo can be taken with or without food (a low-fat meal is recommended). Dietary habits around the time of Everolimus /placebo intake should be as consistent as possible throughout the study. If vomiting occurs, no attempt should be made to replace the vomited dose. All dosages prescribed and dispensed to the patient and all dose changes during the study must be recorded.

Medication labels will comply with US legal requirements and be printed in English. They will supply no information about the patient. The storage conditions for study drug will be described on the medication label.

For this trial, Everolimus and placebo are supplied, by Novartis, 10 tablets per card. Tablets should be opened only at the time of administration as drug is both hygroscopic and light-sensitive. Drug request forms will be provided to use when ordering Everolimus and placebo. Everolimus will only be shipped once all required regulatory documents are received.

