**Table 3-6 Examples of clinically relevant drug interaction: substrates, inducers and inhibitors of isoenzyme CYP3A.**

Substrates (competitive inhibition)	
Antibiotics  : clarithromycin* erythromycin telithromycin*	Calcium Channel Blockers: amlodipine diltiazem felodipine nifedipine nisoldipine nitrendipine verapamil
Anti-arrhythmics: quinidine	HMG CoA Reductase Inhibitors  : atorvastatin cerivastatin lovastatin simvastatin
Benzodiazepines: alprazolam diazepam midazolam triazolam	Miscellaneous: aprepitant buspirone haloperidol methadone pimozide quinine sildenafil tamoxifen trazodone vincristine
Immune Modulators: cyclosporine tacrolimus (FK506)	
HIV Protease Inhibitors: indinavir* ritonavir* saquinavir*	
Prokinetic: cisapride	
Antihistamines: astemizole chlorpheniramine30	
Inducers	
Carbamazepine Phenobarbital Phenytoin* Rifabutin*	Rifampin* St John's wort Troglitazone
Inhibitors	
Amiodarone Cimetidine Clarithromycin Delavirdine Diltiazem Erythromycin Fluvoxamine* Grapefruit juice Sevilla orange	Indinavir Itraconazole* Ketoconazole* Voriconazole* Posaconazole* Mibepridil Nefazodone* Nelfinavir* Troleandomycin Verapamil

Based on: Ingelman-Sundberg M, Human drug metabolising cytochrome P450 enzymes: properties and polymorphisms, Naunyn Schmiedebergs Arch Pharmacol. 2004 Jan;369(1):89-104. and [<http://www.medicine.iupui.edu/flockhart/clinlist.htm> as of July 13, 2006]

\* asterisk denotes strong inhibition/ induction

Please note:

- strong inhibitor implies that it can cause  $\geq 5$ -fold increase in AUC or  $\geq 80\%$  decrease in clearance of sensitive CYP substrates
- moderate inhibitor implies that it can cause 2 to 5-fold increase in AUC values or 50-80% decrease in clearance of sensitive CYP substrates.

(Distinction is not always categorical as interaction can vary according to conditions).

1. Macrolide antibiotics: Azithromycin is not a CYP3A substrate. It may therefore be employed where antibiotic therapy with a macrolide is desirable in a patient being treated with **Everolimus**
2. Statins: Atorvastatin and pravastatin may be administered with **Everolimus**, since a PK interaction study has shown that there is no relevant PK interaction.

- Seville orange, star fruit, grapefruit and their juices affect P450 and PgP activity. Concomitant use should be avoided

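### Section 3.3.3 classes the same CYP3A4 inducers differently in three places, with different dosing actions, and its 2.5 mg step does not fit the 5 mg tablets described

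*Combined protocol and SAP*

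**What the plan says.** Section 3.3.3 deals with CYP3A4 inducers in three places.

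- **Bullet list under Concomitant therapy.** Of strong agents it says: "inducers (such as rifampin, rifabutin) should be avoided. Provided there is no alternative treatment available, patients should be closely monitored for potential toxicities". Of moderate ones it says: "moderate CYP3A4 inducers (e.g. carbamazepine, phenobarbital, phenytoin) should also be avoided if possible, or used subject to caution". Two examples of caution follow in brackets: "increased frequency of safety monitoring, temporary interruption of Everolimus". Neither bullet mentions raising the everolimus dose.
- **Subsection on inducers of CYP3A4 and/or PgP.** It first tells sites to avoid strong inducers. It then continues: "If patient requires co-administration of strong CYP3A4 inducers (i.e., phenytoin, carbamazepine, rifampin, rifabutin, phenobarbital, St. John's wort), an increase in the dose" of everolimus, to no more than double the dose in use, should be considered, "using 2.5mg - 5mg increments". The first step comes 7 days after the inducer starts. A further step may follow after another 7 days if no safety concern has appeared. The subsection acknowledges that no clinical data support this adjustment.
- **Table 3-6.** Its key reads "asterisk denotes strong inhibition/ induction". Among the inducers, phenytoin, rifabutin and rifampin carry the asterisk. Carbamazepine, phenobarbital, St John's wort and troglitazone do not.

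On supply, section 3.3.1 describes a "once daily dose of 10 mg (two 5 mg tablets", packed ten tablets to a card. The documents mention neither a 2.5 mg tablet nor tablet splitting.

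**The concern.** The class given to an inducer decides what a site is told to do. Take a patient who must start phenytoin. The bullet list leads to caution, with closer monitoring or a temporary hold as examples. The subsection leads to considering a stepwise increase. Two sites could each follow the protocol and handle the same patient differently.

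The first issue is patient safety: an increase that the protocol itself says lacks clinical data should not depend on which paragraph is read. The second is exposure. Sites are blinded, so the ambiguity meets patients in both arms, but it can change drug exposure only in the everolimus arm.

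The 2.5 mg step raises a separate practical question, whether a site could dispense the doses that the subsection describes.

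**Working it through.** No sample size, power or event count is involved. The check is a comparison of the three sources, followed by simple arithmetic on tablets.

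**Step 1. Classification, source by source.**

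| Inducer | Bullet list, 3.3.3 | Inducers subsection, 3.3.3 | Table 3-6 |
|---|---|---|---|
| Carbamazepine | moderate | strong | not marked strong |
| Phenobarbital | moderate | strong | not marked strong |
| Phenytoin | moderate | strong | strong |
| Rifampin | strong | strong | strong |
| Rifabutin | strong | strong | strong |
| St John's wort | not named | strong | not marked strong |

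- Bullet list against subsection: 3 of the 3 drugs named as moderate are strong in the subsection.
- Table 3-6 against the bullet list: they differ on phenytoin.
- Table 3-6 against the subsection: they differ on carbamazepine, phenobarbital and St John's wort.

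No two of the three sources agree throughout.

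**Step 2. Action attached to each class.**

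| Class | Bullet list | Inducers subsection |
|---|---|---|
| Moderate inducer | avoid if possible, or caution (examples: more monitoring, temporary hold) | no action given |
| Strong inducer | avoid; close monitoring if there is no alternative | avoid; if required, consider an increase to at most double |

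The difference is therefore not only one of labels. For rifampin and rifabutin, which both texts call strong, only the subsection mentions an increase.

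**Step 3. Does anything else settle it?** The notes to Table 3-6 define strong and moderate for inhibitors only, so there is no criterion for inducers. The cross-references do not help. Section 3.3.3 sends the reader to Table 3-5 for CYP3A4 inducers, but Table 3-5 covers pneumonitis. Section 1.1.3.1 points to Table 3-3, whereas the table of CYP3A examples is numbered 3-6.

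**Step 4. Dose steps in whole 5 mg tablets.** Inputs: tablet 5 mg (section 3.3.1); starting points 10 mg and 5 mg daily (Table 3.0); increments of 2.5 or 5 mg and a cap of twice the prior dose (subsection). Tablets needed = dose ÷ 5.

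| Start | Increment | After one step | After two steps | Cap |
|---|---|---|---|---|
| 10 mg | 5 mg | 15 mg (3 tablets) | 20 mg (4 tablets) | 20 mg |
| 10 mg | 2.5 mg | 12.5 mg (2.5 tablets) | 15 mg (3 tablets) | 20 mg |
| 5 mg | 5 mg | 10 mg (2 tablets) | already at the cap | 10 mg |
| 5 mg | 2.5 mg | 7.5 mg (1.5 tablets) | 10 mg (2 tablets) | 10 mg |

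Steps of 5 mg work from both starting points and reach the cap. A single 2.5 mg step gives 12.5 or 7.5 mg, and neither is a whole number of tablets.

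**The case against.** Three objections carry weight.

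**The two texts are not flatly contradictory orders.** A reader might infer that the protocol orders an interruption in one place and a doubling in the other, so that a patient on 10 mg could be required to take anything from 0 to 20 mg. The documents do not support that. Both texts begin with avoidance. The temporary hold is one of two examples of caution, in a sentence that also covers moderate inhibitors, and section 3.2.4 limits any dose delay to 21 days. The increase is only to be considered, and it goes stepwise with a safety condition before the second step. A site could monitor more often and also consider an increase. This stands: 0 to 20 mg is what the wording permits at its extremes, not a clash of mandates. It does not remove the mismatch, because the bullet list never mentions an increase and the class labels conflict.

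**The dose steps are mostly feasible.** A reader might infer that the increases cannot be dispensed at all. Step 4 shows otherwise: only the 2.5 mg end of the range fails. Section 3.3.1 also does not say outright that no other strength can be ordered. It simply describes none. The introduction mentions marketed 5 mg and 10 mg tablets, and these would not give a 2.5 mg step either.

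**Table 3-6 is weaker evidence.** It offers examples, assigns no dosing action, and notes that the distinction is not always clear-cut. A missing asterisk in a table read from PDF is less secure than running text. That is fair, but the conflict between the bullet list and the subsection does not depend on the table.

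**Conclusion.** The inconsistency is real and rests on the wording of section 3.3.3 itself. Three inducers are moderate in one text and strong in another, with different actions. Table 3-6 agrees fully with neither. For two further inducers, strong in both texts, only one text adds a dose increase. Nothing elsewhere in the documents resolves this.

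The tablet point is narrower. The 2.5 mg increment cannot be made with the whole 5 mg tablets described, while the 5 mg increment can. This assumes that tablets are not split and that no other strength is supplied, since none is described.

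The effect on the trial cannot be sized, because the documents give no count of patients likely to need these drugs. The number is probably small, and nothing here is shown to affect the primary comparison of progression-free survival. The point should be corrected as a matter of safety instruction.

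**What to change.** The sponsor should reconcile the bullet list, the inducers subsection and Table 3-6 into one classification, with one stated action per class. If the strong and moderate classes are kept, the protocol should say what defines them for inducers. The increments in the subsection should be reconciled with the tablet strength described in section 3.3.1. The cross-references to Tables 3-3 and 3-5 should be corrected at the same time. Which classification or dose rule stands is for the sponsor to decide; no view is taken here. The cost is a protocol wording amendment, with no change to sample size, endpoints or analysis.

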**Table 3-6 Examples of clinically relevant drug interaction: substrates, inducers and inhibitors of isoenzyme CYP3A.**

Substrates (competitive inhibition)	
Antibiotics  : clarithromycin* erythromycin telithromycin*	Calcium Channel Blockers: amlodipine diltiazem felodipine nifedipine nisoldipine nitrendipine verapamil
Anti-arrhythmics: quinidine	HMG CoA Reductase Inhibitors  : atorvastatin cerivastatin lovastatin simvastatin
Benzodiazepines: alprazolam diazepam midazolam triazolam	Miscellaneous: aprepitant buspirone haloperidol methadone pimozide quinine sildenafil tamoxifen trazodone vincristine
Immune Modulators: cyclosporine tacrolimus (FK506)	
HIV Protease Inhibitors: indinavir* ritonavir* saquinavir*	
Prokinetic: cisapride	
Antihistamines: astemizole chlorpheniramine30	
Inducers	
Carbamazepine Phenobarbital Phenytoin* Rifabutin*	Rifampin* St John's wort Troglitazone
Inhibitors	
Amiodarone Cimetidine Clarithromycin Delavirdine Diltiazem Erythromycin Fluvoxamine* Grapefruit juice Sevilla orange	Indinavir Itraconazole* Ketoconazole* Voriconazole* Posaconazole* Mibepridil Nefazodone* Nelfinavir* Troleandomycin Verapamil

Based on: Ingelman-Sundberg M, Human drug metabolising cytochrome P450 enzymes: properties and polymorphisms, Naunyn Schmiedebergs Arch Pharmacol. 2004 Jan;369(1):89-104. and [<http://www.medicine.iupui.edu/flockhart/clinlist.htm> as of July 13, 2006]

\* asterisk denotes strong inhibition/ induction

Please note:

- strong inhibitor implies that it can cause  $\geq 5$ -fold increase in AUC or  $\geq 80\%$  decrease in clearance of sensitive CYP substrates
- moderate inhibitor implies that it can cause 2 to 5-fold increase in AUC values or 50-80% decrease in clearance of sensitive CYP substrates.

(Distinction is not always categorical as interaction can vary according to conditions).

1. Macrolide antibiotics: Azithromycin is not a CYP3A substrate. It may therefore be employed where antibiotic therapy with a macrolide is desirable in a patient being treated with **Everolimus**
2. Statins: Atorvastatin and pravastatin may be administered with **Everolimus**, since a PK interaction study has shown that there is no relevant PK interaction.

- Seville orange, star fruit, grapefruit and their juices affect P450 and PgP activity. Concomitant use should be avoided

- No chronic treatment with systemic steroids (at a dose equivalent of greater than 20 mg prednisone per day) or other immunosuppressive agents. Topical or inhaled corticosteroids are allowed.
- The use of live vaccines and close contact with those who have received live vaccines should be avoided during treatment with everolimus. Examples of live vaccines include intranasal influenza, measles, mumps, rubella, oral polio, BCG, yellow fever, varicella and TY21a typhoid vaccines.

Oral anticoagulants such as warfarin are CYP2C9 substrates and, as such, no interaction with everolimus is expected. However, drug-drug interaction studies between macrolide antibiotics and warfarin have produced mixed outcomes and the disparity in these findings has led to the conclusion that multiple factors may alter the clearance of warfarin. The coadministration of everolimus and oral anticoagulants is possible but should be subject to verification of coagulation (INR) once steady state is reached (after one week's treatment).

Examples are provided in Table 3-5 (CYP3A4 inhibitors/inducers) and Table 3-6 (Drug interactions mediated by P-glycoprotein). A comprehensive list of cytochrome P450 isoenzymes and CYP3A4 inhibitors, inducers, and substrates can be found at <http://medicine.iupui.edu/flockhart>. This website is continually revised and should be checked frequently for updates.

### **3.3.4 Treatment compliance**

Records of study medication used, dosages administered, and intervals between visits will be recorded during the study. Drug accountability will be noted and patients will be asked to return all unused study medication. A drug diary should be given to each patient to complete (see Appendix B)

### **3.3.5 Definition of Curative Intent Therapy for Locally Advanced Squamous Cell Carcinoma of the Head and Neck**

Specific curative intent therapy is left to the discretion of investigators but the following criteria should be met for patients to be considered to have received curative intent therapy for locally advanced SCCHN and to be eligible for study:

- Acceptable chemoradiotherapy regimens:
  - Cisplatin or carboplatin based regimens
  - 5FU/hydroxyurea based regimens
  - Cetuximab based regimens
- Radiotherapy dose to gross disease must be > 58 Gy if treated post-operatively and > 64Gy if treated with primary chemoradiotherapy or radiotherapy alone
- Neoadjuvant or induction chemotherapy is permitted

- Any questions regarding the acceptability of curative intent therapy should be directed to [name] ([name]) or [name] ([name])

### 3.4 Visit schedule and assessments

#### 3.4.1 Pre-study Procedures

- All patients must have completed curative intent therapy for locally advanced SCCHN 8-16 weeks prior to randomization (as defined in 3.3.5 AND be NED as defined in 3.2.2).
- Tissue must have been collected **PRIOR** to starting curative intent therapy on all patients (see Section 3.4.7)
- A detailed assessment of hepatitis B/C medical history and risk factors must be done for all patients at screening.

Testing for hepatitis B viral load and serologic markers: HBV-DNA, HBsAg, HBs Ab, and HBc Ab and HCV RNA PCR are required at screening for all patients in the following risk categories:

- All patients who currently live in (or have lived in) Asia, Africa, Central and South America, Eastern Europe, Spain, Portugal, and Greece.  
[<http://wwwnc.cdc.gov/travel/yellowbook/2010/chapter-2/hepatitis-b.aspx#849> ]
- Patients with any of the following risk factors:
  - known or suspected past hepatitis B infection,
  - blood transfusion(s) prior to 1990,
  - current or prior IV drug users,
  - current or prior dialysis,
  - household contact with hepatitis B infected patient(s),
  - current or prior high-risk sexual activity,
  - body piercing or tattoos,
  - mother known to have hepatitis B
  - history suggestive of hepatitis B infection, e.g., dark urine, jaundice, right upper abdomen pain.
- Additional patients at the discretion of the investigator

Testing for hepatitis C should be performed using quantitative RNA-PCR at screening for all patients in the following risk categories:

- known or suspected past hepatitis C infection (including patients with past interferon 'curative' treatment),
- blood transfusions prior to 1990,
- current or prior IV drug users,
- current or prior dialysis,
- household contact of hepatitis C infected patient(s),
- current or prior high-risk sexual activity,
- body piercing or tattoos,

- At the discretion of the investigator, additional patients may also be tested for hepatitis C.

